## **9.0 Criteria for Removal from the Study**

9.1 Patients will be considered to have failed therapy if they develop evidence of pulmonary infection secondary to RSV (documented by chest radiographic study and/or Oxygen saturation level less than 90 mm Hg on room air). Therapy could be stopped or could be changed to either the standard or the modified regimen of aerosolized ribavirin if the patient is on the oral schedule and changed to the standard or continued on the modified regimen of aerosolized ribavirin if the patient is on the aerosolized regimen; all at the discretion of the primary care service. IVIG 500mg/kg every other day for 4 doses or Synagis (palivizumab) 15mg/kg as a single dose can be used in combination with aerosolized ribavirin.

9.2 Adverse events to ribavirin requiring discontinuation of therapy are: deterioration of respiratory function, abnormal liver function tests ( $>5$  x the upper normal limits), frequent bronchospasms not responding to bronchodilators, hypotension and cardiac arrest.

9.3 Anemia may occur due to ribavirin and therapy would be discontinued if there is evidence of severe hemolysis and/or the patient develops severe anemia as per the NCI classification i.e. Hemoglobin below 8 g/dl for more than 48 hours and does not respond to blood and/or blood products transfusion.

## 10.0 Cost Analysis

All patients who receive aerosolized ribavirin have to be hospitalized for the entire duration of the therapy, or even more depending on the patient condition. Patients who will be treated with oral ribavirin may be hospitalized at the discretion of the primary service. An average per day cost of keeping patients in hospital for ribavirin administration will be obtained from the financial department and institutional records and will be used to calculate the total cost of treating patients with ribavirin using the following formula:

Total cost of treating the patients with ribavirin (aerosolized or oral) = cost of keeping the patient in-hospital per day for RSV  $\times$  total number of days the patient is kept in hospital + cost of the drug (aerosolized and oral ribavirin) and its administration (for aerosolized ribavirin).

This will be compared to the total cost of administering oral ribavirin on an outpatient basis by adding the total cost of the drug and the follow up visits. In either arm of the study, if a patient progresses to pneumonia, the total cost of treating the patient with aerosolized ribavirin (if applicable) will be calculated using the above formula and added to the total cost.

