## Protocol Body

### 1.0 Objectives

Primary Objectives:

[figure not shown]
1) To determine whether oral ribavirin given for therapy of Respiratory Syncytial Virus (RSV) upper respiratory tract infection (URI) can prevent its progression to Lower respiratory tract Infection (LRI)-pneumonia, when compared to aerosolized ribavirin – modified regimen in HSCT recipients at moderate or high risk for progression.

Secondary Objectives:

- 1) To determine the safety of oral ribavirin therapy when compared to aerosolized ribavirin.
- 2) To calculate the cost effectiveness of using oral ribavirin when compared to aerosolized ribavirin.
- 3) To compare RSV viral loads in nasal washes and/or other respiratory specimens and RSV neutralizing antibodies in serum between patients on both arms of the study and a observational arm where low risk patients for progression are not receiving either regimen of ribavirin.

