### *Analysis*

We will use descriptive statistics to summarize the demographic and clinical characteristics of patients in each treatment arm and the observational arm.

We will use the Cochran-Mantel-Haenszel test stratified by risk group to test the null hypothesis stated above. We will also estimate the treatment failure rates with exact 95% binomial confidence intervals for each treatment arm.

We will tabulate adverse events for each treatment arm by severity and relationship to study therapy.

We will use descriptive statistics to summarize the costs associated with each treatment arm. Costs for each patient will be calculated as described in section 10.0 above.

We will use descriptive statistics to summarize the RSV viral loads and neutralizing antibodies for each treatment arm and the observational arm.

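### Cost effectiveness is a stated objective, but the costing rule leaves out part of pneumonia care, its comparison sentence does not fit the by-arm summary, and cost is never related to failures

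*Combined protocol and SAP*

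**What the plan says.** Section 1.0 lists as secondary objective 2: "To calculate the cost effectiveness of using oral ribavirin when compared to aerosolized ribavirin".

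Section 10.0 supplies the costing rule. On place of care, aerosol patients are inpatients throughout ("All patients who receive aerosolized ribavirin have to be hospitalized for the entire duration of the therapy"), while for the oral arm "Patients who will be treated with oral ribavirin may be hospitalized at the discretion of the primary service". The inpatient formula covers both drugs: "Total cost of treating the patients with ribavirin (aerosolized or oral) = cost of keeping the patient in-hospital per day for RSV", multiplied by days in hospital, plus drug and, for aerosol, its administration. The next sentence reads: "This will be compared to the total cost of administering oral ribavirin on an outpatient basis", with outpatient cost made up of drug and follow-up visits. For pneumonia in either arm the rule is: "the total cost of treating the patient with aerosolized ribavirin (if applicable) will be calculated using the above formula". That amount then goes on top of the patient's other costs.

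Section 9.1 lets therapy be stopped or changed after failure, at the primary service's discretion, and says of IVIG and palivizumab that either "can be used in combination with aerosolized ribavirin". Section 5.0 also names both as options once LRI develops, and rules both out as treatment of the URI itself.

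Section 11.0, Analysis, states: "We will use descriptive statistics to summarize the costs associated with each treatment arm". It takes each patient's cost from Section 10.0. It plans nothing further on cost.

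**The concern.** Three gaps stand between the objective and the analysis.

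- **Incomplete failure cost.** The pneumonia add-on is tied to aerosolized ribavirin. Other permitted RSV pneumonia care has no term in the formula.
- **Unclear comparison.** Section 10.0 describes a contrast between an inpatient total and outpatient oral treatment. Whether an oral patient is admitted is decided after randomisation and presumably depends on how ill the patient is, so that contrast does not have the protection of randomisation. Section 11.0 groups costs by arm. The two sections do not clearly describe the same comparison.
- **No link to effect.** Cost effectiveness needs cost and failures to be considered together. The plan only describes cost.

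Cost is a main reason for the trial: Section 2.0 argues that oral treatment could avoid many admissions and save a great deal. In a non-inferiority design oral may be cheaper and still have somewhat more pneumonia, and that is the case in which failure costs and the cost-failure link matter most.

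**Working it through.** **Inputs.** Section 11.0, Sample Size: failure 20% (aerosol) and 15% (oral), margin 10 points, 38 per arm, 1-sided alpha 0.20, power 80%. The plan states no figure for the cost analysis, so the only figure to reproduce is the sample size.

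**Sample size.** n = (0.8416 + 0.8416)² × (0.20×0.80 + 0.15×0.85) / (0.10 + 0.05)² = 2.833 × 0.2875 / 0.0225 = 36.2, so 37 per arm for a fixed design. With the two stated nominal levels (0.6040 and 0.2116), overall alpha is 0.2000 and power at 38 per arm is 80.3%. The stated 38 is sound.

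**Step 1: what the pneumonia rule counts.**

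| Care after pneumonia allowed by Section 9.1 | Counted by the Section 10.0 add-on? |
|---|---|
| Aerosolized ribavirin: drug, administration, hospital days | Yes |
| IVIG or palivizumab given with it | No term |
| Therapy stopped, pneumonia managed without aerosol | No rule |

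Let c be the mean uncosted amount per failure. The undercount per randomised patient is p × c, where p is the arm's failure rate. If c is the same in both arms, the error in the cost difference (oral minus aerosol) is proportional to the difference in failure rates: 0.15c − 0.20c = −0.05c at the planned rates, and 0.30c − 0.20c = +0.10c at the margin. The documents give no value for c. Because care after failure is discretionary, c may also differ between arms.

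**Step 2: what the comparison sentence would estimate.** Let A be the mean aerosol cost, I the mean for hospitalised oral patients, U the mean for outpatient oral patients, and h the share of oral patients hospitalised. Arms are of equal size.

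- By-arm saving: A − [hI + (1−h)U].
- Reading 1, aerosol against outpatient oral only: A − U. This differs from the by-arm saving by h(I − U), which is above zero whenever I exceeds U.
- Reading 2, all inpatients on either drug against outpatient oral, as the formula literally allows: (A + hI)/(1 + h) − U. This differs from the by-arm saving by h[(I − U) − (A − I)/(1 + h)], which can have either sign.

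Sign check for reading 2. The assumptions below are not from the documents, except the $50,000 aerosol drug cost (lower end of the Section 2.0 range): h = 0.5, 10 inpatient days, oral drug $1,000, visits $1,000, pneumonia costs ignored.

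- $2,000 per day: A = 70,000, I = 21,000, U = 2,000. By arm: 70,000 − 11,500 = $58,500. Reading 2: 80,500/1.5 − 2,000 = $51,667, which is lower.
- $4,000 per day: A = 90,000, I = 41,000, U = 2,000. By arm: 90,000 − 21,500 = $68,500. Reading 2: 110,500/1.5 − 2,000 = $71,667, which is higher.

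These figures show only that the direction is not fixed. They do not estimate the size of any bias. If no oral patient is hospitalised (h = 0), both readings equal the by-arm saving.

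**Step 3: cost against failures.** Expected failures are 38 × 0.15 = 5.7 (oral) and 38 × 0.20 = 7.6 (aerosol), or 1.9 fewer on oral. At the margin they are 11.4 against 7.6, or 3.8 more on oral. Cost and failures could therefore point in opposite directions, and no rule is given for weighing them. A ratio of cost to failures averted would be unstable: the standard error of the failure difference is √(0.2875/38) = 0.087, larger than the expected difference of 0.05.

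**The case against.** The strongest reply is that Section 11.0 already settles the grouping: costs are computed per patient and summarised by treatment arm, and Section 10.0 only says how to cost each kind of patient. On that view the comparison sentence is just the costing rule for oral outpatients. This is a natural reading, and it defeats the inference that costs will be compared by place of care instead of by arm. What remains is that Section 10.0 explicitly announces a different comparison, so the two sections need reconciling.

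A reader might also infer that pneumonia is costed as drug alone. It is not: the formula applied after pneumonia includes hospital days and administration. For patients already in hospital, the main formula may also capture bed-days whatever the later treatment. The gap is IVIG, palivizumab, and pneumonia managed without aerosol, most clearly in a patient who was being treated as an outpatient. IVIG and palivizumab are optional under Section 9.1, so the amount may be modest.

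Finally, failure rates and costs are both reported by arm, so anyone could set them side by side, and a phase II screening trial with about 6 to 8 failures expected per arm cannot support a precise ratio. Both points stand. They argue against requiring a ratio. They do not supply an analysis for an objective that is worded as cost effectiveness.

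**Conclusion.** The concern holds as a gap in a secondary objective. The costing rule omits permitted pneumonia care, the comparison sentence conflicts with or is unclear against the by-arm summary, and no planned analysis relates cost to failures. The undercount grows with the number of failures. If the uncosted amount per failure is equal across arms, the error in the cost difference runs from −0.05c at the planned rates to +0.10c at the margin, with c unknown. No money figure can be supported from the documents.

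Two stronger conclusions are tempting and should not be drawn. One is that the objective cannot be answered without bias: a by-arm comparison of the costs as defined is available from Section 11.0, and the missing link to failures is an omission, not a bias. The other is that the comparison favours oral: that follows under one reading if outpatient treatment is cheaper, but under the literal pooled reading the direction can go either way.

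The sample size and the primary analysis are unaffected. This is a cheap improvement.

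**What to change.** **Section 10.0.** State that every randomised patient's total cost is counted: bed-days, visits, study drug and its administration, and all RSV pneumonia treatment, including IVIG and palivizumab and care given without aerosol. Name one follow-up window that applies to both arms, since Section 10.0 sets none. State that costs are compared by randomised arm whatever the place of care, and show inpatient and outpatient costs only as a breakdown.

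**Section 11.0, Analysis.** Report the mean cost difference between arms with a bootstrap 95% CI, next to the difference in failure rates. Incremental cost per pneumonia averted is optional, given its instability. The alternative is to reword objective 2 as a descriptive cost comparison.

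**Cost.** A few more cost items per failing patient and a little more analysis. Section 7.5 already records medications used to treat LRI, and Section 10.0 already draws on the financial department and institutional records.

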## 11.0 Statistical Considerations

This is a randomized phase II non-inferiority screening trial following the principles described by Rubinstein et al. (2005). Our primary outcome for this trial is progression to lower respiratory tract infection (i.e., pneumonia) by day 14 after the completion of therapy. Patients who are found to have pneumonia by day 14 after completion of therapy will be considered treatment failures. Patients who have not developed pneumonia by day 14 after completion of therapy will be considered treatment successes.

### *Randomization*

Patients will be randomized to either aerosolized ribavirin (standard therapy) or oral ribavirin (experimental therapy) using the CORE patient registration system. Block randomization will be utilized and stratified by risk of progression (moderate versus high).

### *Sample Size*

We expect that 20% of patients randomized to aerosolized ribavirin will be considered treatment failures, and we expect that 15% of patients randomized to oral ribavirin will be considered treatment failures. With a non-inferiority margin of 10%, a sample size of 38 patients per

treatment arm will yield 80% power to reject the following null hypothesis with a 1-sided significance level of 0.20:

$$H_0: \pi_{\text{oral}} - \pi_{\text{aerosol}} \geq 0.10$$

$$H_1: \pi_{\text{oral}} - \pi_{\text{aerosol}} < 0.10$$

where  $\pi_{\text{aerosol}}$  is the treatment failure rate for aerosolized ribavirin and  $\pi_{\text{oral}}$  is the treatment failure rate for oral ribavirin. We expect to enroll these patients over 2 winter seasons.

This sample size calculation includes an interim analysis for futility using the methods of Lan and DeMets (1983) with an O'Brien-Fleming (1979) stopping boundary. The futility analysis will be conducted once 38 patients have been evaluated for treatment failure. We expect the timing of this futility analysis to be after the first winter season of the study. The nominal significance level for this futility analysis is 0.6040, and the nominal significance level at the end of the study is 0.2116.

This sample size calculation was performed using East 5.2 (Copyright © 2008, Cytel Inc., Cambridge, MA).

For the observational arm, up to 20 patients will be enrolled for a total of 96 patients for the whole trial.

### *Analysis*

We will use descriptive statistics to summarize the demographic and clinical characteristics of patients in each treatment arm and the observational arm.

We will use the Cochran-Mantel-Haenszel test stratified by risk group to test the null hypothesis stated above. We will also estimate the treatment failure rates with exact 95% binomial confidence intervals for each treatment arm.

We will tabulate adverse events for each treatment arm by severity and relationship to study therapy.

We will use descriptive statistics to summarize the costs associated with each treatment arm. Costs for each patient will be calculated as described in section 10.0 above.

We will use descriptive statistics to summarize the RSV viral loads and neutralizing antibodies for each treatment arm and the observational arm.

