Alternatively, many patients have been treated with oral ribavirin with particularly encouraging results (*Figure above*). This drug has been approved by the Food and Drug Administration (FDA) in combination with interferon alfa-2b for the treatment of Hepatitis C and it is commercially available in generic form. Although oral ribavirin was adopted as part of the armamentarium for therapy of RSV infection in immunocompromised patients in many centers in the US and Europe, further trials are necessary to demonstrate its efficacy and safety. A recent study done in Basel, Switzerland reported a total of 19 HSCT patients treated with oral ribavirin, of these 11 patients had URI, while 8 had LRI. A decrease in RSV viral loads of 2 log10 copies/mL within 7 days after treatment initiation was seen in 11 patients and none progressed to LRI or died. Another 6 patients reported a mean decrease in RSV load of 2 log10 copies/mL within 14 days of diagnosis, LRI occurred in 2 patients and 1 died. The authors also found that the rate of disease progression and mortality rate to be comparable to studies evaluating aerosolized ribavirin (*Khanna et al, CID 2008:46 407*). They further concluded that prospective, multicenter studies are needed to identify effective antiviral treatment for RSV infection among immunocompromised patient groups, where systemic ribavirin could be an option.

A systematic evaluation of oral ribavirin as an alternative therapeutic regimen for RSV infection needs to be explored. A double blind randomized comparative trial is not feasible due to the relatively small number of HSCT patients with this infection every year on the national level. We would like to conduct this phase II randomized trial to evaluate the efficacy and safety of oral ribavirin for prevention of RSV LRI when compared to aerosolized regimen ("modified regimen"). If oral use of ribavirin is as effective as the aerosolized regimen, this would be immensely beneficial to the patients as it would make the administration of ribavirin easier and more convenient and may prevent hospitalization in a good proportion of patients with tremendous impact on cost savings. Furthermore, it may increase its use and also encourage its early use in the therapy of RSV URI, which may have a favorable impact on overall morbidity and mortality in our immunocompromised patients.

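### The primary test named for the non-inferiority null is Cochran-Mantel-Haenszel, an equality test with no place for the 10-point margin; run as named it has about 40% power, not 80%

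*Combined protocol and SAP*

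**What the plan says.** Section 11.0 opens with "This is a randomized phase II non-inferiority screening trial". Under Sample Size, the null is that the oral failure rate minus the aerosol failure rate is at least 0.10, and 38 patients per "treatment arm will yield 80% power to reject the following null hypothesis with a 1-sided significance level of 0.20". The planning rates are 20% failure on aerosol and 15% on oral. One futility look takes place at 38 evaluated patients: "The nominal significance level for this futility analysis is 0.6040, and the nominal significance level at the end of the study is 0.2116".

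Under Analysis, the primary test is a single sentence: "We will use the Cochran-Mantel-Haenszel test stratified by risk group to test the null hypothesis stated above". The only interval estimates planned for the primary outcome are separate ones for each arm: "We will also estimate the treatment failure rates with exact 95% binomial confidence intervals for each treatment arm".

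Section 2.0 describes the result that would be useful: "If oral use of ribavirin is as effective as the aerosolized regimen, this would be immensely beneficial to the patients".

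**The concern.** The hypothesis and the test do not match. The null is a risk difference of 10 points or more. The ordinary CMH statistic compares observed with expected failures on the assumption that the arms do not differ in either stratum, so a 10-point allowance cannot enter it. No other part of the plan supplies the link: there is no stratified difference, no shifted statistic, and no confidence limit to compare with 0.10. The nominal levels are given, but the statistic they apply to is not, nor is it said whether the futility stop is binding.

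If an analyst follows the sentence and runs CMH one-sided in favour of oral, the trial asks whether oral is better. Section 2.0 says it is enough for oral to be as good. A trial that went as planned could then fail its primary analysis. If the analyst instead works out that a margin test was meant, the estimator, standard error and decision limit must be chosen later, in an open-label trial.

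**Working it through.** **Inputs (section 11.0, Sample Size).** Failure rates 0.20 aerosol and 0.15 oral; margin 0.10; 38 per arm; look at 38 of 76 patients (information fraction 0.5, taken as 19 per arm); nominal one-sided levels 0.6040 and 0.2116. The corresponding normal cut-offs are c1 = −0.2637 and c2 = 0.8009.

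**Step 1: reproduce the plan's sample size.** Unpooled variance term: 0.20×0.80 + 0.15×0.85 = 0.2875. The distance from the margin is 0.10 + 0.05 = 0.15. For a fixed design, n = (0.8416 + 0.8416)² × 0.2875 / 0.15² = 36.2, so 37 per arm. At 38 per arm, SE = √(0.2875/38) = 0.0870.

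With the look, success means passing both cut-offs: P(Z1 > c1 and Z2 > c2), where Z1 and Z2 are normal with means θ√0.5 and θ, unit variance and correlation √0.5.

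- Margin statistic: θ = 0.15/0.0870 = 1.72, power **80.3%**.
- At the null boundary, θ = 0 and alpha is **0.2000**.

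The stated design is therefore that of a risk-difference test against 0.10, with a futility stop that is followed.

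**Step 2: the same design with an equality statistic.** The shift is now 0.05, so θ = 0.05/0.0870 = 0.575 and power is **39.2%**. If the margin statistic is used at the look and CMH only at the end, power is 40.9%.

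**Step 3: other true rates, and an exact check.** SE is 0.0918 at 20%/20% and 0.0987 at 30%/20%. The exact column enumerates all two-stage binomial outcomes (19 + 19 per arm, one stratum, CMH without continuity correction). CMH ranges cover both choices of interim statistic.

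| True oral / aerosol failure | Margin test: formula (exact) | CMH: formula (exact) |
|---|---|---|
| 15% / 20% | 80.3% (81.6%) | 39.2–40.9% (40.1–42.1%) |
| 20% / 20% | 59.2% (60.3%) | 20.0–21.1% (20.7–22.0%) |
| 30% / 20% | 20.0% (19.7%) | 3.2–3.5% (3.2–3.5%) |

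An equality test at these two levels would need about 339 per arm for 80% power.

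**Step 4: one worked final result, single stratum.** Oral 6/38, aerosol 8/38 failures.

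- Margin: RD = −2/38 = −0.0526; SE = 0.0887; Z = (0.10 + 0.0526)/0.0887 = 1.720; p = 0.043. The upper one-sided 78.84% limit is −0.0526 + 0.8009×0.0887 = 0.018, below 0.10. Non-inferiority is shown.
- CMH: expected oral failures 14/2 = 7; variance 38²×14×62/(76²×75) = 2.893; Z = (7 − 6)/√2.893 = 0.588; p = 0.278. This misses 0.2116.

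With 8/38 aerosol failures, the margin test passes with up to 8 oral failures (p = 0.142 at 8, 0.220 at 9). CMH passes only with 5 or fewer (p = 0.182 at 5, 0.278 at 6).

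**Step 5: does stratification change this?** The plan does not give the mix of risk groups. *Assumption:* stratum failure rates were taken from the treated columns of the table in section 2.0 (12/85 moderate, 5/15 high), rescaled to 20% overall, or set to 20% in both strata, with 3 to 9 high-risk patients among each 19 per arm. That table covers any therapy at the URI stage, not aerosolized ribavirin specifically. In simulations of 300,000 trials per case, the stratified risk-difference test had 81–85% power and CMH 40–43% for every mix tried.

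**The case against.** The sentence does not say that CMH will test equality. It refers back to the stated null, the trial is labelled non-inferiority, and the sample size uses the margin. On that reading the 80% is correct and the plan only leaves out the form of the statistic. This is very probably what was intended. It does not rescue the sentence, because the test it names does not test that null, and standard CMH output gives a p-value for a different hypothesis.

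The 40% is also conditional. The Analysis text gives neither sidedness nor continuity correction. One-sided is a fair inference from the Sample Size text. In an exact single-stage check at level 0.2116, one-sided CMH has 42% power uncorrected and 31% corrected; two-sided it has 26% and 16%. With the correction, even 5 against 8 failures fails (p about 0.27). So about 40% is the figure most favourable to CMH.

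Finally, with no decision rule written down, a non-significant CMH result might be read as non-inferiority. With true rates of 30% and 20% and no interim look, non-significance occurs in about 42% of trials (one-sided for harm at 0.2116) to 58% (two-sided at 0.2116), against the intended 20%. That would be a separate misuse, but the present wording does not rule it out.

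**Conclusion.** The concern holds and should be fixed before analysis. The named statistic does not test the stated null, and nothing else in the plan says how the 10-point margin is applied. The sample size and nominal levels are right for a margin-based test and are not in question.

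Run as named, power at the planning rates is about 40% instead of 80%. With truly equal 20% rates, about 1 trial in 5 would succeed instead of about 3 in 5. These figures assume a one-sided test in favour of oral and no continuity correction; they do not depend materially on the risk-group mix. Used that way, CMH does not inflate false claims (about 3% success when oral is 10 points worse). The loss is in power and in an unanswered primary question.

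**What to change.** Replace the primary-test sentence in the Analysis text with wording to this effect:

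> The null hypothesis will be tested with the Mantel-Haenszel risk difference (RD, oral minus aerosol) stratified by risk group, with a stratified standard error (for example Sato): Z = (0.10 − RD)/SE, one-sided p = 1 − Φ(Z). The same statistic is used at both looks. At 38 evaluated patients the trial stops for futility if p > 0.6040; this rule is binding. At the end, non-inferiority is declared if p ≤ 0.2116, that is, if the upper one-sided 78.84% confidence limit for RD is at or below 0.10. RD will be reported with its confidence interval.

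CMH may stay as a supplementary test of equality.

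The binding status needs stating because the final level of 0.2116 depends on it: alpha is 0.2000 if the stop is followed and 0.2116 if it is overridden. If the sponsor wants freedom to override, a final level of 0.20 keeps alpha at 0.20, with 79.3% power when the stop is followed.

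The cost is one paragraph. With the binding rule, no patients, data, sample size or boundaries change.
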